### Follow-up of Adverse Events

All investigators should follow up on subjects with SAEs and AEs of special interest until the event is resolved or until, in the opinion of the investigator, the event is stabilized or determined to be chronic. All other non-serious AEs will be followed until the subject exits the study. Details of AE resolution must be documented in the eCRF.

#### Documentation and Reporting of Adverse Events

Adverse events should be reported and documented in accordance with the procedures outlined below. All AEs occurring during the study must be documented on the relevant eCRF pages. The following data should be documented for each AE:

- Description of the symptom event
- Classification of 'serious' or 'not serious'
- Severity
- Date of first occurrence and date of resolution (if applicable)
- Action taken
- Causal relationship
- Outcome of event (unknown, recovered, not yet recovered, recovered with sequelae, death [with date and cause reported])

### 7.1.2.1.1 Serious Adverse Events

### Serious Adverse Event Definition

An SAE is any untoward medical occurrence or effect that, at any dose,

- Results in death.
- Is life-threatening (an AE is life-threatening if the subject was at immediate risk of death from the event as it occurred, ie, it does not include a reaction that might have caused death if it had occurred in a more serious form).
- Requires or prolongs inpatient hospitalization. (Complications occurring during hospitalization are AEs and are SAEs if they cause prolongation of the current hospitalization. Hospitalization for elective treatment of a pre-existing non-worsening condition is not, however, considered an AE. The details of such hospitalizations must be recorded on the medical history or physical examination page of the eCRF).
- Results in persistent or significant disability/incapacity. An AE is incapacitating or disabling if it results in a substantial and/or permanent disruption of the subject's ability to carry out normal life functions.
- Results in a congenital anomaly/birth defect.

Allergan considers all cancer AEs as SAEs. Any abortion (spontaneous or nonspontaneous) is also considered a SAE.

In addition, medical and scientific judgement is required to decide if prompt notification is required in situations other than those defined for SAEs above. This may include any event that the investigator regards as serious that did not strictly meet the criteria above but may have jeopardized the subject or required intervention to prevent one of the outcomes listed above, or that would suggest any significant hazard, contraindication, side effect, or precaution that may be associated with the use of the study drug.

#### **Reporting of Serious Adverse Events**

Any SAE must be reported by the investigator if it occurs during the clinical study or within 30 days of receiving the study drug, whether or not the SAE is considered to be related to the study drug. An SAE report consists of the SAE form, the AE form, and the concomitant medication form. A copy of these forms must be faxed **within 24 hours** for the attention of the medical monitor at:

[contact] Back-Up [contact] E-mail: [contact]

The investigator should not wait to receive additional information to document fully the event before notification of a SAE, though additional information may be requested. Where applicable, information from relevant laboratory results, hospital case records, and autopsy reports should be obtained.

Instances of death, congenital abnormality, or an event that is of such clinical concern as to influence the overall assessment of safety, if brought to the attention of the investigator at any time after cessation of study drug administration and linked by the investigator to this study, should be reported to the study monitor.

The sponsor and/or INC Research will promptly notify all relevant investigators and the regulatory authorities of findings that could adversely affect the safety of subjects, impact on the conduct of the study or alter the independent ethics committee (IEC)/institutional review board (IRB) approval/favorable opinion of the study. In addition, INC Research, on behalf of the sponsor, will expedite the reporting to all concerned investigators, to the IECs/IRBs, where required, and to the regulatory authorities of all adverse reactions that are both serious and unexpected.

Details of the procedures to be followed if a pregnancy occurs are provided in Section 5.5.4.

#### 7.1.2.1.2 Suspected Unexpected Serious Adverse Reactions

#### **Suspected Unexpected Serious Adverse Reaction Definition**

An adverse event is considered "unexpected" if it is not listed in the Reference Safety Information (RSI), such as Investigator Brochure, Prescription Information (eg, the current package insert for Rhofade), or it is not consistent with the risk information described in any of the RSI. If an unexpected AE is serious and suspected, it is a suspected unexpected serious adverse reaction (SUSAR).

All SUSARs will be the subject of expedited reporting. The sponsor and/or INC Research shall ensure that all relevant information about a SUSAR is reported to the relevant competent authorities and IEC/IRB within 15 days after knowledge by the sponsor of such a case. All investigators should follow up on SUSARs until the event is resolved or until, in the opinion of the investigator, the event is stabilized or determined to be chronic. Post study SUSARs that occur after the subject has completed the clinical study must be reported by the investigator to the sponsor.

# 7.1.2.2 Urine Pregnancy Test (Females of Childbearing Potential Only)

Females of child bearing potential will have urine pregnancy tests performed at the timepoints indicated in Table 1. A negative test result must be obtained during screening and prior to energy-based treatment at the baseline visit. If a positive pregnancy test is obtained at any visit during the study the subject will be withdrawn from the study.

Females of childbearing potential are defined as any female subject after puberty. Females that are postmenopausal (defined as having 12 months of consecutive spontaneous amenorrhea) or surgically sterile (6 months post-surgical bilateral oophorectomy with or without hysterectomy, 6 months post-hysterectomy, or 6 months post-tubal ligation) are exempt from this requirement.

# 7.1.2.3 Vital Signs

Vital signs (blood pressure, pulse rate, and oral body temperature) will be recorded (at the timepoints listed in Table 1) in a standardized manner (ie, after the subject has rested in the sitting position for 5 minutes).

Changes in vital signs determined by the investigator to be clinically significant will be noted as an AE in the eCRF. Such abnormalities will be closely monitored until stabilized or resolved.

# 7.1.2.4 Physical Examination

Physical examinations (evaluating eyes, ears, nose, mouth, throat, thyroid, lungs, heart, abdomen, extremities, neuromuscular system, skin, and lymph nodes) will be performed at the timepoints specified in Table 1.

Significant changes from baseline examination on screening will be recorded as AEs.

# 7.1.2.5 Clinician's Telangiectasia Assessment

The investigator will use the CTA to evaluate the average overall severity of telangiectasia on the subject's face using the 5 point scale below (at the timepoints specified in Table 1). The investigator performing the assessment should record the results in the eCRF and should not compare the current assessment to previous assessments to prevent bias.

	Clinician Telangiectasia Assessment (CTA)	
Grade	Description	
0	Clear skin with no signs of telangiectasia	
1	Almost clear, a few barely visible telangiectasia	
2	Mild, a few visible telangiectasia	
3	Moderate, with presence of clearly visible telangiectasia	
4	Severe, with the presence of many visible telangiectasia	
# 7.1.2.6 Dermal Tolerability Assessment

Dermal Tolerability Assessments will be performed by both investigator and subject at the timepoints specified in Table 1.

### Investigator's Assessments: Dryness and Scaling of the Treatment Area

Investigators will assess dryness and scaling in the treatment area using the 4-point scales below. The results will be recorded in the eCRF and should not be discussed with the subject.

Dryness: skin roughness			
Score	Grade	Description	
0	None	No dryness	
1	Mild	Slight but definite roughness	
2	Moderate	Moderate roughness	
3	Severe	Marked roughness	

Scaling: abnormal peeling of the stratum corneum			
Score	Grade	Description	
0	None	No peeling	
1	Mild	Barely perceptible peeling, noticeable only on light scratching or rubbing	
2	Moderate	Obvious, but not profuse peeling	
3	Severe	Heavy scale production	

# Subject's Assessments: Stinging/Burning and Pruritus of the Treatment Area

The investigator will ask the subject if he/she is experiencing burning/stinging and pruritus (itching) using the 4-point scales below. The results will be recorded in the eCRF.

Stinging/Burning: prickling pain sensation			
Score	Grade	Description	
0	None	No stinging/burning	
1	Mild	Slight warm, tingling/stinging sensation; not really bothersome	
2	Moderate Definite warm, tingling/stinging sensation; somewhat bothersome		
3	Severe	Hot, tingling/stinging sensation that has caused definite discomfort	

Pruritus: itching in the application area			
Score	Grade	Description	
0	None	Normal, no itching in the application area	
1	Mild	Noticeable discomfort causing intermittent awareness	
2	Moderate	Noticeable discomfort causing continuous awareness	
3	Severe	Definite, continuous discomfort interfering with normal daily activities	

# 7.1.3 Other Assessments

# 7.1.3.1 Demographic Information and Medical History

At the screening visit, subject demographic data will be collected. These data include date of birth, age, gender, race, and ethnicity. A medical history will also be obtained from each subject at this visit. Medical history includes a detailed history of prior cosmetic and surgical procedures, with start and stop dates, if applicable, as well as any discontinuations due to intolerability or toxicity.

# 7.1.3.2 Fitzpatrick Phototyping Scale

Each subject's skin phototype will be assessed at screening by the investigator using the Fitzpatrick Phototyping Scale in the table below:

Fitzpatrick skin type	Constitutive or unexposed skin color	Sunburn and tanning history a
Ι	Ivory white (pale white) Extremely fair skin	Burns easily, strongly; never tans
Π	White or fair skin	Burns easily; tans minimally with difficulty
III	Medium white skin	Burns moderately; tans moderately and uniformly
IV	Beige or lightly tanned or olive skin	Burns minimally; tans easily and moderately
V	Moderate brown or tanned brown skin	Rarely burns; tans profusely (dark brown)
VI	Dark brown or black skin	Never burns, tans profusely (dark brown or black)

a Sunburn and tanning history is based on what subjects say their responses are to an initial sun exposure (eg, about 45 to 60 minutes of noon exposure in early summer). The subject response should be based on the following 2 specific questions:

- 1. "How painful is your sunburn (intensity of erythema, edema, skin peeling and discomfort) after 24 hours?"
- 2. "How much tan will you develop in a week?"

# 8 STATISTICAL METHODS

#### 8.1 General Statistical Considerations

A brief summary of the general statistical analysis methods is provided below; full details will be provided in a separate statistical analysis plan, which will be finalized prior to database lock.

Data will be summarized using descriptive statistics (number of observations [n], mean, standard deviation, median, minimum, and maximum for continuous variables; and n and percentage for categorical variables).

Two critical timepoints, baseline and end of study, will be referenced in most of statistical analyses for this study. Baseline is defined as the latest assessment prior to any study treatments for each subject (Day 1). End of study is the last clinical visit an enrolled subject has in this study (Day 56 exit visit). Subjects who discontinue will be asked to return for the last clinical visit (Day 56 exit visit) for end-of-study data collection.

#### 8.1.1 Datasets or Populations Analyzed

The following analysis populations will be used:

- Enrolled all subjects who signed an ICF and enrolled in the study.
- Modified intent-to-treat (mITT) all subjects treated with both study drug and energy-based therapy who had at least one post-treatment efficacy assessment between Day 3 and Day 56.
- Safety all subjects who received at least one dose of study drug as treatment in this study.

Allergan		06 Feb 2018
CMO-MA-MED-0530	Version 2	Page 39 of 59

The enrolled population will be used for subject disposition, demographics, and baseline characteristics summaries; the modified intent-to-treat population will be used for the efficacy analyses, and the safety population will be used for safety analyses.

# 8.1.2 Demographic and Other Baseline Characteristics

The number of subjects in each of the analyzed study populations will be described. Subjects who discontinue study drug or are removed from the study prematurely will also be reported. Reasons for study drug and/or energy-based therapy discontinuation, and time of withdrawal from the study will be described.

Subject characteristics at entry into the study will be summarized in frequency tables and descriptive statistics will be provided for quantitative variables.

Concomitant medications will be coded by means of the World Health Organization Drug Dictionary (WHODrug) dictionary into Anatomical Therapeutic Chemical (ATC) classification codes. The type and timing of use of specific concomitant medications will be listed and summarized. The type and duration of pre-study use will be described on the safety population. The type, dose, schedule, duration of use, dose modifications, dose omissions, and reasons for deviations from initial therapy will be described.

# 8.1.3 Efficacy Variables and Analysis

The efficacy variables are:

- The number and percentage of subjects with at least a 1-grade decrease (improvement) on the CEA, from baseline over a 6-hour period following study drug application at each study visit and timepoint (specified in Table 1).
- Percentage change from baseline at each visit in rosacea facial redness using DIA of standardized facial photographs.
- Proportion of subjects indicating Satisfied or Very Satisfied (score of 3 or 4) with treatment on the Items from Subject Satisfaction Assessment for Rosacea Facial Redness and proportion of subjects indicating Somewhat Satisfied and Very Satisfied with treatment on the FACE-Q Satisfaction with Skin Scale at each visit and timepoint specified in Table 1.

The proportion of subjects with at least a 1-grade decrease (improvement) on the CEA from baseline (ie, predose on Day 1) will be summarized by visit and timepoint using frequency distributions. In addition, the raw CEA data will be summarized by visit and timepoint using descriptive statistics. Each item from the PROs (Items from Subject Satisfaction Assessment for Rosacea Facial Redness and FACE-Q Satisfaction with Skin Scale) will be summarized using frequency distributions by visit and timepoint.

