# 4.3 Clinical Studies

To date thus far there have been 4 human dermal safety studies and 10 clinical studies (including 3 pivotal Phase 3 studies) of topical dermal oxymetazoline for the treatment of persistent facial erythema associated with rosacea. All clinical studies have been conducted with the same cream formulation with varying concentrations of oxymetazoline.

In the first 2 Phase 3 studies oxymetazoline HCl cream 1.0% was applied topically for 29 days, once daily, to the faces of patients with persistent, moderate, or severe facial erythema associated with rosacea, followed by a 28 day post-treatment period. The results from these 2 pivotal studies consistently demonstrated that oxymetazoline HCl cream 1.0% was safe and well tolerated based upon multiple safety evaluations, and was significantly more effective than vehicle in reducing facial erythema associated with rosacea over a 12-hour evaluation period (hours 3, 6, 9, and 12) following a 29 day treatment period. In the most recent Phase 3 study the long-term safety and efficacy of oxymetazoline HCl cream 1.0% (applied topically, once daily) was evaluated in 440 patients with moderate to severe persistent facial erythema associated with rosacea over a period of 52 weeks. Improvement in erythema was consistently observed 3 and 6 hours after study drug application compared with predose assessments from Day 1 through to Week 52 of the treatment period.

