# 5.2 Exploratory Endpoints

The exploratory endpoints of the study are:

- The number and percentage of subjects with at least a 1-grade improvement on the CEA from baseline over a 6-hour period (measured at hours 1, 3, and 6) following study drug application.
- Percentage change from baseline in rosacea facial redness using DIA of standardized facial photographs during the treatment period.
- Proportion of subjects indicating Satisfied or Very Satisfied with treatment on the Items from Satisfaction Assessment for Rosacea Facial Redness and proportion of subjects indicating Somewhat Satisfied or Very Satisfied with treatment on the FACE-Q Satisfaction with Skin Scale.

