2.2 Visit and Timepoint Windows

There is no plan to programmatically derive visit/timepoint windows. The scheduled visits/timepoints as recorded on the electronic Case Report Form (CRF) will be directly taken as the analysis visits/timepoints and will be used in reporting and analyses. The analysis visits include the Screening Visit, the Baseline (Day 1) Visit, the Day 3 Visit, the Day 29 Visit, the Day 31 Visit and the Day 56 (Exit Visit). The analysis timepoints corresponding to each visit on and after Day 1 include the Pre-Dose and the Post-Dose. Also refer to Table 1 Schedule of Assessments and Procedures (page 18) of the Protocol (Oct 12, 2017) for scheduled visits/timepoints.

If there are multiple observations of same assessment within the same scheduled visit/timepoint window, all values of multiple observations will be included for listing, but only the mean value of multiple observations will be used for the by-visit/timepoint summary or analysis. Assessment outside the scheduled visit/timepoint window will be marked as unscheduled assessment, and will be used for listing only.

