5.2 Analyses of Efficacy Variable(s)

There is no statistical testing of hypotheses pertaining to efficacy variables. Statistical inference will be limited to the construction of distribution-free 95% CI for the median percentage change from baseline variables, since these percentage change variables are known for the deviation from normality in distribution. The distribution-free 95% CI for the

median will be calculated using SAS[®] procedure Proc Univariate. In this section, summary tables mainly in the forms of descriptive statistics will be presented for the above-specified efficacy and patient reported outcomes (PRO) variables.

- The number and percentage of subjects with at least a 1-grade improvement on the CEA from baseline, by visit/timepoint.
- Summary statistics of CEA by visit/timepoint.
- Proportion of subjects indicating Satisfied or Very Satisfied with treatment on the Items of Satisfaction Assessment for Rosacea Facial Redness, by visit. There are two items (questions). See Appendix 14.2 of the Protocol. Item 1 (Question 1) is: Right now, how satisfied are you with the appearance of your facial redness? Item 2 (Question 2) is: Right now, how satisfied are you with the appearance of the amount of redness on your face? This summary will be repeated for each of the two items.
- Proportion of subjects indicating Somewhat Satisfied or Very Satisfied with treatment on the FACE-Q Satisfaction with Skin Scale, by visit. There are 12 questions on the FACE-Q Satisfaction assessments regarding the subjects' rating of their satisfaction with skin. See Appendix 14.3 of the Protocol. This summary will be repeated for the response to each of the 12 questions, and for the average response to the 12 questions.
- Percentage change from baseline in rosacea facial redness using Digital Image Analysis (DIA) of standardized facial photographs, by visit/timepoint. This summary table will be presented if the rosacea facial redness data are obtained and such facial redness can be quantified. This summary table for the percentage change from baseline in rosacea facial redness will be provided.

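### CEA and DIA changes are measured only from Day 1 before the first energy session; a change from same-day predose should be added to describe the acute effect of the cream

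*Protocol*

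**What the plan says.** **Reference.** Protocol 8.1 sets a single baseline: "Baseline is defined as the latest assessment prior to any study treatments for each subject (Day 1"). SAP 2.3.2 agrees: a measure with one reading before the first energy session uses that reading. CEA and photography are such measures.

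**CEA.** Protocol 5.2 words the endpoint as improvement "from baseline over a 6-hour period (measured at hours 1, 3, and 6) following study drug application". Protocol 8.1.3 fixes the reference: "The proportion of subjects with at least a 1-grade decrease (improvement) on the CEA from baseline (ie, predose on Day 1) will be summarized". The summary covers each visit and each timepoint within it. SAP 5.2 lists "The number and percentage of subjects with at least a 1-grade improvement on the CEA from baseline, by visit/timepoint".

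**DIA.** SAP 5.2 lists "Percentage change from baseline in rosacea facial redness using Digital Image Analysis (DIA) of standardized facial photographs, by visit/timepoint", if redness can be quantified. SAP 5.2 also plans a distribution-free 95% CI for the median percentage change.

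**Schedule.** Energy sessions are on Days 1 and 29, and cream starts on Day 3 (Protocol synopsis and 5.3). Table 1 takes CEA and photographs at predose, 1, 3 and 6 h on Days 3, 31 and 56, and before treatment and at 1 h on Days 1 and 29.

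**Timepoint labels.** SAP 2.2: "The analysis timepoints corresponding to each visit on and after Day 1 include the Pre-Dose and the Post-Dose".

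**Purpose.** The opening of SAP section 5 gives the aim as evaluating the effect of daily cream used as an adjunct to energy-based therapy. SAP 5.3, on other efficacy analyses, is marked not applicable. Neither document defines a change from same-day predose.

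**The concern.** The energy sessions act on the outcome being measured: Protocol 4.5 and 5.6.7 say they reduce erythema. The study has a single arm, so no concurrent group shows what the sessions do alone. A subject who drops a grade after a session and gets nothing from the cream is still a responder at hours 1, 3 and 6 of a cream visit. The endpoint wording would lead a reader to credit that response to the cream.

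The readings that would separate the two within a visit are already scheduled. Protocol 4.3 describes the long-term Phase 3 result as improvement "consistently observed 3 and 6 hours after study drug application compared with predose assessments", so a postdose-against-predose comparison is familiar in this programme.

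A smaller point concerns labels. No cream is applied on Day 1 or Day 29, and Day 29 falls inside the washout. Yet Protocol 8.1.3 speaks of response after cream at every Table 1 visit and timepoint, and SAP 2.2 names the timepoints at all visits from Day 1 as pre-dose and post-dose. Read literally, the 1 h readings on Days 1 and 29, which follow an energy session, appear as post-dose response.

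At stake is how clearly the exploratory objective is answered. The primary safety analysis and the sample size are not affected.

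**Working it through.** The plan gives no efficacy figure to reproduce. Its only calculated figure, N = 43, concerns treatment-related adverse events. The documents give no size for either effect on CEA, so all effect sizes below are assumptions.

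**1. What each reading follows**

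| Visit | Sessions so far | Same-day predose CEA and photographs | Planned reference |
|---|---|---|---|
| Day 3 | 1 | yes | Day 1, before session 1 |
| Day 31 | 2 | yes | Day 1, before session 1 |
| Day 56 | 2 | yes | Day 1, before session 1 |

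**2. Noise-free illustration.** Let a proportion L improve one grade from the energy sessions and a proportion C improve one grade from the cream, independently, with no worsening.

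- Day 1 responder rate at predose: L
- Day 1 responder rate after cream: 1 − (1 − L)(1 − C)
- Visible rise: C(1 − L)
- Response against same-day predose: C

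| L | C | Predose | After cream | Rise | Same-day |
|---|---|---|---|---|---|
| 0.50 | 0 | 50% | 1 − 0.5×1 = 50% | 0 points | 0% |
| 0.50 | 0.30 | 50% | 1 − 0.5×0.7 = 65% | 15 points | 30% |
| 0.70 | 0.30 | 70% | 1 − 0.3×0.7 = 79% | 9 points | 30% |

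The rise is smaller than C by the factor (1 − L), because a subject who already responds at predose cannot become a responder again.

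**3. With rating noise.** A simulation of 300,000 subjects used latent severity with mean 3.2 and SD 0.5, rating noise with SD 0.35 grade, scores rounded to 0–4, and entry at CEA 3 or more. Entries are the share with at least a 1-grade change at a postdose hour; the predose column is the share at predose.

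| Energy effect (grade) | Cream effect (grade) | Predose vs Day 1 | Postdose vs Day 1 | Improved vs same-day predose | Worsened vs same-day predose |
|---|---|---|---|---|---|
| 0 | 0 | 21% | 21% | 18% | 18% |
| 0.5 | 0 | 54% | 54% | 19% | 19% |
| 1.0 | 0 | 85% | 85% | 19% | 19% |
| 0 | 0.5 | 21% | 54% | 49% | 4% |
| 0.5 | 0.5 | 54% | 85% | 50% | 4% |
| 1.0 | 0.5 | 85% | 98% | 50% | 4% |

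- With an inert cream, the Day 1 rate after cream runs from 21% to 85% with the energy effect. The same-day rate stays at 18–19%, matched by equal worsening. The 21% with no effect at all reflects rating noise and selection at entry.
- With the same half-grade cream effect, the visible rise is 54 − 21 = 33, 85 − 54 = 31 and 98 − 85 = 13 points. Same-day improvement minus worsening is 49 − 4 = 45, 50 − 4 = 46 and 46 points.

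**4. What the planned tables give.** The mean CEA shift from predose to each hour can be computed from the by-timepoint summaries, provided the same subjects contribute at both (SAP 2.3.2 uses observed cases). In the noise-free case that shift equals C, 0.30 grade in the last two rows of step 2. It identifies the proportion improving only if nobody worsens and nobody moves more than one grade. For DIA, let p and q be a subject's percentage changes from Day 1 at predose and postdose. The same-day change is 100 × [(1 + q/100)/(1 + p/100) − 1]. It needs both values for each subject, and its median and CI do not follow from the two separate medians.

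**The case against.** A reader might infer that the planned tables cannot tell a useful cream from an inactive one. The documents do not support that. Predose is an analysis timepoint and CEA is tabulated by timepoint, so an inert cream would give a flat profile (50% and 50% in step 2), and mean CEA can be compared in aggregate.

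A reader might also infer that both measures are labelled as response after cream. Only the protocol's CEA wording says so. The DIA endpoint refers to the treatment period or to each visit, and the SAP, which supersedes the protocol on discrepancies, drops the phrase from its CEA item. Nor does Protocol 4.3 say that the long-term study used same-day predose; that is one reading of its sentence.

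The proposed contrast has its own weaknesses. With imperfect grading it shows about 18–19% improving on an inert cream, under the noise assumed above. It captures only the acute effect, while the SAP's interest is daily application. Day 56 predose may hold carry-over from daily cream. Days 3 and 31 fall two days after a session, when post-treatment erythema may still be resolving (Protocol 4.5 says a day or two), and any further fading over 6 h would count as cream response.

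The Day 29 label is partly explained by Table 1 and Protocol 6.3, which tie predose on Days 1 and 29 to the energy session. Efficacy is exploratory and untested, and change from Day 1 is a fair description of the combined regimen.

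All of this stands. It narrows the point to a missing within-subject summary and unclear labels; it does not supply that summary.

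**Conclusion.** The point holds as a worthwhile, low-cost improvement to an exploratory analysis. CEA response and DIA change use only the reading before the first session, so postdose results at cream visits reflect energy-based therapy plus cream. Aggregate predose-to-postdose comparison will be possible, but the difference in Day 1 responder rates understates acute response when predose response is high: 9 points against 30% in the noise-free case with L = 0.70 and C = 0.30, and 13 points against a net 46 in the noisy case with a one-grade energy effect. These sizes rest wholly on assumed effects and noise; the direction follows from the definition of a responder. The within-subject proportion improving after cream, and the median same-day DIA change with its CI, are not planned.

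It would be too strong to conclude that same-day predose isolates the cream's true effect, or that the Day 1 comparison should be dropped. The study has no control arm, and neither reference replaces one.

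**What to change.** Amend SAP 5.2, with a matching label change in SAP 2.2:

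1. Keep the Day 1 comparison and title it as the combined effect of energy-based therapy plus cream.
2. For Days 3, 31 and 56, at 1, 3 and 6 h, add the number and percentage with at least a 1-grade CEA improvement from same-day predose, and beside it the number and percentage with at least a 1-grade worsening, so that rating noise is visible.
3. If DIA redness can be quantified, add percentage change from same-day predose at the same timepoints, with the distribution-free 95% CI for the median already planned.
4. Label the 1 h readings on Days 1 and 29 as following energy-based therapy, not as post-dose.
5. State the limits with the tables: acute effect only, possible resolving post-session erythema on Days 3 and 31, possible carry-over at Day 56 predose, and no control arm.

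The cost is two exploratory tables and SAP wording, with no new visits or readings. The SAP allows amendments before database lock and supersedes the protocol on discrepancies, so the change can be made there. Editing Protocol 5.2 or 8.1.3 as well would need ethics committee approval under Protocol 11.1.
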